parameters of the cohort of elderly adults (test) vs. non-elderly adults (reference) with PK data in a 16 to 24 ratio and a between-subject coefficient of variation (CV) of 60%, the 90% confidence interval (CI) of the geometric mean ratio (GMR) for minimum plasma concentration (C_{\min}) would be predicted to have a half-width of 35%, indicating that we can be 90% confident that the true GMR is in the interval observed GMR/1.35 to 1.35*GMR. If 90 subjects were enrolled with 60 on active treatment in a 24 to 36 ratio, the predicted half-width would be 28%.

For the safety objective of the study, the sample size of 40 to 60 subjects treated with JNJ-63623872 can be characterized by assessing the precisions for (potentially) observed treatment-emergent AEs. For example, if no related treatment-emergent serious adverse event (SAE) is observed in a sample of 60 subjects exposed to JNJ-63623872, it can be concluded with 95% confidence that the true incidence of related treatment-emergent SAEs will be less than 5%.

The primary PK analysis will be done on the PK-evaluable population, defined as all subjects who received active study treatment (JNJ-63623872 and oseltamivir), with evaluable PK measurements on Day 3.

Descriptive statistics will be used for all endpoints and will be tabulated by treatment arm and age cohort. No formal statistical hypothesis testing will be performed. Subgroup analyses may be summarized descriptively using baseline characteristics.

Primary Endpoint

- PK parameters of JNJ-63623872 (ie, C_{\min} , C_{\max} , and AUC_{12h}) established on Day 3.

Secondary Endpoints

1. The proportion of subjects experiencing AEs, SAEs, and treatment-emergent grade 1-4 laboratory abnormalities.
2. Time to return to usual activity and usual health (Questions 5 and 9 of the additional items for the Flu-PRO).
3. Time to significant reduction in influenza symptom severity.
4. Proportion of subjects with a significant reduction (to mild or none for all influenza symptoms) at each assessment.
5. Disease status and incidence of complications associated with influenza after the start of study treatment, and disease progression:
 - bacterial pneumonia (culture confirmed where possible),
 - other bacterial superinfections,
 - respiratory failure,
 - pulmonary disease (eg, COPD),
 - cardiovascular and cerebrovascular disease (eg, myocardial infarction, CHF, arrhythmia, stroke).
6. Duration and severity of clinical symptoms as measured by the Flu-PRO.

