11. STATISTICAL METHODS

Statistical analysis will be done by the sponsor or under the authority of the sponsor. A general description of the statistical methods to be used to analyze the efficacy and safety data is outlined below. Specific details will be provided in the Statistical Analysis Plan.

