The FLU-PRO and Flu-iiQ™ domain scores will be presented descriptively over time using descriptive statistics. A linear mixed model will be used to analyze composite symptom scores over time, per domain. For the Flu-iiQ™ a daily score will be derived averaging observed scores before the analysis. Baseline subject characteristics will be included (in particular baseline score) in case these provide to be predictive of post-baseline scores. Mean differences between treatment arms will be derived from this model using appropriate contrasts and will be presented including the associated 95% CI. For both measures, an AUC of composite symptom scores over a 7- and 14-day period per domain will be calculated and compared using a mixed model for repeated measurements.

Other PRO endpoints that will be analyzed are:

1. Time to return to usual activity and usual health (Questions 5 and 9 of the additional items for the Flu-PRO).
2. Time to significant reduction in influenza symptom severity.
3. Proportion of patients with a significant reduction (to mild or none for all influenza symptoms) at each assessment.

Other Outcomes

The length of overall hospital stay will be calculated from the date of first study drug intake up to the date of discharge. Subjects still hospitalized at the end of the study will be censored at the last contact. Data will be presented using Kaplan-Meier curves. For a comparison between treatment arms, the time to hospital discharge in days will be analyzed using an accelerated failure time model (if the data provide an acceptable model fit) or alternatively a Cox proportional hazards model (in case the hazards are proportional). Additionally, the time to event data will be analyzed using the Gehan-Wilcoxon method. The time to resumption of normal daily activities will be analyzed in an analogous fashion.

Resistance Analyses

The results of viral sequencing and phenotyping will be evaluated by the sponsor virologist. Additional exploratory characterization of the viral genotype and phenotype may be performed and will be reported accordingly.

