Data will be presented using Kaplan-Meier curves and Kaplan-Meier estimates by treatment group, overall and by age group. For a comparison between treatment arms, the time to parameters will be analyzed using an accelerated failure time model. The model will use the parametric shape, selected based on the goodness of fit criterion (AIC), and may take a Weibull, log-logistic, lognormal, or gamma distribution. As baseline covariates the respective baseline composite impact scores and age category (≥ 18 - < 65 years, ≥ 65 - ≤ 85 years) will be included. If the data don't provide an acceptable model fit, alternatively a Cox proportional hazards model can be used (in case the hazards are proportional). In case a Cox proportional hazards model is used a Log-log plot of survival will be added to check the proportional hazard assumption. Additionally, the time to event data will be analyzed using the logrank test and Gehan-Wilcoxon method.

4.2.5. *FLU-iiQTM Additional Daily Diary Items*

For the 5 additional daily diary items of FLU-iiQTM frequency distributions of the number (%) of subjects per additional FLU-iiQTM item and per response category will be shown at baseline and all post-baseline assessments, per treatment group.

4.2.6. *Influenza Patient Reported Outcome Diary (FLU-PRO)*

- **FLU-PRO total score and FLU-PRO domain scores**

The FLU-PRO total score is computed as a mean score across 32 items contained by the instrument. Total scores can range from 0 (symptom free) to 4 (very severe symptoms).

Six FLU-PRO domain scores are computed, representing symptom severity in each of the following body areas: Nose, Throat, Eyes, Chest/Respiratory, Gastrointestinal and Body/Systemic. Each domain score is calculated as the mean of all items comprising the domain, see also Table 8. Each FLU-PRO domain score ranges from 0 to 4.

These scores will be calculated at each time point a questionnaire was filled. A change from baseline will also be calculated.

The FLU-PRO scores and changes from baseline will be presented descriptively over time.

Table 8: FLU-PRO domain scores

Domain	Items	Scoring and Minimum Data Requirement
Nose	Runny or dripping nose Congested or stuffy nose Sneezing Sinus pressure	Arithmetic mean of 4 items Daily score for 3 of 4 items must be present to calculate domain score

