The time to significant reduction in influenza symptom severity (to mild or none for all influenza symptoms) is defined as time in hours from the first dose of investigational product until the first of 2 successive recordings in which the total score for each of the 2 recordings are lower or equal to 1 and all the domain scores are lower or equal to 1. The 2 successive recordings should have been done within 3 scheduled successive analysis timepoints (one missing in between is allowed).

Censoring will be done similar to the FLU-PRO time to return to usual activity and time to return to usual health as specified above.

Data will be presented using Kaplan-Meier curves and Kaplan-Meier estimates. For a comparison between treatment arms, the time to significant reduction in influenza symptom severity will be analyzed using an accelerated failure time model. The model will use the parametric shape, selected based on the goodness of fit criterion (AIC), and may take a Weibull, log-logistic, lognormal, or gamma distribution. As baseline covariate the age category (≥ 18 - < 65 years, ≥ 65 - ≤ 85 years) and baseline FLU-PRO total score will be included. If the data don't provide an acceptable model fit, alternatively a Cox proportional hazards model can be used (in case the hazards are proportional). In case a Cox proportional hazards model is used a Log-log plot of survival will be added to check the proportional hazard assumption. Additionally, the time to event data will be analyzed using the logrank test and Gehan-Wilcoxon method.

- **Proportion of patients with a significant reduction in influenza symptom severity.**

The proportion of subjects with a significant reduction in symptom severity (the total score for each of the 2 recordings are lower or equal to 1 and all the domain scores are lower or equal to 1) at each assessment will be tabulated.

4.2.7. *FLU-iiQTM Additional Daily Diary Items*

For the 9 additional daily diary items of FLU-PRO frequency distributions of the number (%) of subjects per additional FLU-PRO item and per response category will be shown at baseline and all post-baseline assessments, per treatment group.

4.2.8. *Correlation between viral load, viral titer and changes in clinical symptoms*

- **Correlation between the decline in viral load, the decline in viral titer and clinical symptoms**

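### SAP 4.2.6 labels the FLU-PRO symptom-reduction endpoint as every symptom mild or absent but scores it on domain means, and its proportion version adds a two-recording condition that the protocol does not have

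*SAP*

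**What the plan says.** SAP 4.2.6 introduces the time endpoint with the words "significant reduction in influenza symptom severity (to mild or none for all influenza symptoms) is defined as time in hours". It then defines the event as the first of two successive recordings, with one missing recording allowed in between, at each of which the total score is "lower or equal to 1 and all the domain scores are lower or equal to 1". The same section says of the six domains: "Each domain score is calculated as the mean of all items comprising the domain". Table 8 gives domains of 3 to 11 items, 32 in all, and each domain score ranges from 0 to 4.

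The proportion endpoint follows. Its definition of success reads "reduction in symptom severity (the total score for each of the 2 recordings" and ends "lower or equal to 1) at each assessment will be tabulated".

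The protocol lists the proportion endpoint in the Synopsis (Secondary Endpoints) as "Proportion of subjects with a significant reduction (to mild or none for all influenza symptoms) at each assessment" and in Section 11.6 as "Proportion of patients with a significant reduction (to mild or none for all influenza symptoms) at each assessment". Neither place names an instrument, an item rule or a pair of recordings. Protocol Section 11 adds: "Specific details will be provided in the Statistical Analysis Plan". The Time and Events Schedule has FLU-PRO completed once daily.

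**The concern.** There are two separate faults.

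First, the label speaks about each symptom and the rule speaks about averages. A reader of the label would take a counted success to mean that no symptom was worse than mild, and a mean of at most 1 does not ensure that. The contrast with SAP 4.2.3 makes this easier to miss. There, Flu-iiQ resolution requires every symptom to score 0 or 1, and SAP 4.2.8 later lists the two endpoints in the same set of clinical measures, although they rest on different kinds of rule.

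Second, the proportion endpoint combines a two-recording condition with tabulation at each assessment. With a once-daily diary the two recordings fall on different days, and the SAP does not say whether a given day is paired with the day before or the day after. Followed literally, the sentence produces a different and lower figure than the protocol's endpoint.

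**Working it through.** The plan gives no figure for either fault, so there is none to reproduce.

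**Label against rule**

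Inputs: item counts from SAP Table 8; items scored 0 to 4; a domain passes when its mean is at most 1, that is, when its item sum is at most n. All items are taken as answered. With a single raised item of score v and the rest at 0, the domain score is v/n. The most items in a domain that can score at least v is the whole-number part of n/v.

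| Domain | n | Lone item at 3 | Lone item at 4 | Most items ≥2 | Most items ≥3 | Most items at 4 |
|---|---|---|---|---|---|---|
| Nose | 4 | 0.75 | 1.00 | 2 | 1 | 1 |
| Throat | 3 | 1.00 | 1.33 (fails) | 1 | 1 | 0 |
| Eyes | 3 | 1.00 | 1.33 (fails) | 1 | 1 | 0 |
| Chest/Respiratory | 7 | 0.43 | 0.57 | 3 | 2 | 1 |
| Gastrointestinal | 4 | 0.75 | 1.00 | 2 | 1 | 1 |
| Body/Systemic | 11 | 0.27 | 0.36 | 5 | 3 | 2 |
| All | 32 | passes for 32 of 32 | passes for 26 of 32 | 14 | 9 | 5 |

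The 26 is 4 + 7 + 4 + 11. The last three columns are upper bounds on what one success can contain; they are not frequencies.

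The total-score condition does not close the gap. If every domain sum is at most n, the overall sum is at most 32 and the total is at most 32/32 = 1.

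The result does not depend on where mild is placed. If an item score of 1 is taken as mild, items at 2 or more can pass. If 2 were taken as mild, items at 3 and 4 can still pass.

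**One recording against two**

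With a common denominator, requiring a second success can only lower the proportion. To size the effect, assume the same success probability p on both days and a day-to-day correlation r. Neither value is in the documents.

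P(both) = p² + r·p(1−p), so the gap to a single recording is p(1−p)(1−r).

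| p (one recording) | Both, r = 0.8 | Both, r = 0.5 | Both, r = 0 |
|---|---|---|---|
| 30% | 25.8% (gap 4.2) | 19.5% (gap 10.5) | 9.0% (gap 21.0) |
| 50% | 45.0% (gap 5.0) | 37.5% (gap 12.5) | 25.0% (gap 25.0) |
| 70% | 65.8% (gap 4.2) | 59.5% (gap 10.5) | 49.0% (gap 21.0) |

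Gaps are in percentage points.

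**The case against.** The case on the other side is substantial, and it rules out several stronger readings.

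- *The time endpoint can be programmed.* This is true. The wording after the label gives one explicit rule, and nothing proposed here changes that endpoint's main analysis. The fault is in what the label claims.
- *A reader might infer that FLU-PRO and the cut-off of 1 are arbitrary.* The documents do not support that. The protocol's neighbouring secondary endpoints use Flu-PRO. SAP 4.2.6 anchors the total from symptom free at 0 to very severe at 4. The overall-severity question in Protocol Attachment 6 scores mild as 1 on a matching 0 to 4 scale. Domain means are a legitimate choice.
- *A reader might infer an undeclared departure from the protocol that belongs in SAP 1.6.* For the domain rule this does not follow, because the protocol set no item rule and left details to the SAP.
- *A reader might infer that two programmers are bound to disagree on the proportion.* That is not established. The SAP is to be read together with the protocol, whose definition is per assessment. The two-recording phrase looks carried over from the time endpoint, and the Data Presentation Specifications, which are not available here, may settle it. The sentence as it stands still says something different from the protocol.
- *The extremes are extreme.* This is accepted. The 25-point gap needs one patient's consecutive diary days to be independent, and the counts of 14, 9 and 5 are ceilings.
- *Some related points are not grounds for change.* The redundant total-score condition alters no result. The diarrhea imbalance in Protocol Section 1.1 comes from a small healthy-volunteer group in which almost all events were mild, so it does not justify a version without the gastrointestinal items.

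**Conclusion.** Both faults stand in limited form. The rule in SAP 4.2.6 does not deliver the meaning in its label: any single item at 3, and 26 of the 32 items at 4, can sit inside a counted success if the other items are at 0. How often this would happen cannot be known from the documents, so a reader should not conclude that counted successes commonly contain severe symptoms.

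The two-recording condition does not belong in the proportion endpoint as the protocol defines it. Its likely cost is about 4 to 5 percentage points if consecutive days are strongly correlated, and more if they are not. That range rests on the assumed p and r, and on equal p on both days, which ignores recovery from one day to the next.

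The consequences are limited. SAP 4.2 states that there is no formal testing, these are secondary endpoints, and SAP 4.2.3 already analyses item-level Flu-iiQ resolution for 7 and for 10 symptoms. The issue affects interpretation and reproducibility. It does not touch error rates or sample size.

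**What to change.** 1. In the proportion endpoint, delete the reference to two recordings and define success on the single assessment, as the protocol does.
2. Keep the domain-mean rule as the main analysis, but name the endpoint for what it measures (all FLU-PRO domain scores ≤1) and carry that name into SAP 4.2.8.
3. Add one of the following:
   - a supportive analysis matching the protocol wording, in which every non-missing scored item is ≤1, with item score 1 taken as mild as a stated assumption; or
   - a table by arm of domain-rule successes with any item ≥2 and with any item ≥3.

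All of this uses data already collected. The cost is a few lines of SAP text and one extra derivation or table. If the supportive analysis is chosen, its events will come later, with somewhat more censoring.

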Descriptive statistics and mean (SE) plots will be shown for the log₁₀ values of viral load and viral titer (qRT-PCR and viral culture) and the changes from baseline calculated in log₁₀ (vp/mL or TCID₅₀/mL).

- **Incidence of influenza A viral negativity by assessment**

The proportion of subjects with a negative viral load and a negative viral titer will be tabulated at each time point. In addition, per parameter and time point a logistic model with baseline viral load/viral titer and age category (≥ 18 - <65 years, ≥ 65 - ≤ 85 years) as covariates will be used to obtain the odds ratios (95% CI) for the comparison of the incidence of influenza A viral negativity of treatment versus placebo.

Stacked barcharts of the percentage of subjects per response category will be made by day and treatment for viral load and viral titer. The following response categories will be used:

- For viral load (log₁₀ vp/mL) measurements:
 - Target not detected (<2.05 log₁₀ vp/mL)

- Target detected ($<2.18 \log_{10} \text{ vp/mL}$)
- Quantifiable ($\geq 2.18 \log_{10} \text{ vp/mL}$)
- For viral titer ($\log_{10} \text{ TCID}_{50}/\text{mL}$) measurements:
 - Negative ($<0.75 \log_{10} \text{ TCID}_{50}/\text{mL}$)
 - Positive ($\geq 0.75 \log_{10} \text{ TCID}_{50}/\text{mL}$)

- **Time to influenza A viral negativity**

The time to influenza A viral negativity will be determined based on nasal MT swabs: a subject will be considered influenza A viral negative at the time point that the first confirmed negative nasal MT swab was recorded (in days) i.e. defined as time in days from start of treatment to first of assessments = 'negative' and the next assessed measurement is not = 'positive' (ignoring missings, i.e. if first 'negative' is last available assessment or if next assessed result after first 'negative' is also 'negative'). If this doesn't occur, a subject will be censored at the time of the last observed nonnegative swab + 1 day. Note that at baseline every subject is considered positive.

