Resolution of influenza symptoms is defined as the first of a successive series of 2 recordings in which all symptom scores for each of the 2 assessments are 0 or 1 for all 7 primary influenza symptoms of the Flu-iiQTM (cough, sore throat, headache, nasal congestion, feeling feverish, body aches or pains, and fatigue (tiredness)). If the first record of a successive series of 2 recordings of resolved influenza is before day 14 in the evening then the 2 successive recordings should have been done over 3 scheduled successive analysis timepoints, 1 missing timepoint is allowed. If the first record of a successive series of 2 recordings of resolved influenza is at or after the evening record of Day 14 then the 2 successive recordings should have been done within 2 scheduled successive analysis timepoints (no missing allowed).

In cases where there are no sufficient recordings of resolved influenza as defined above, the endpoint will be censored. Censoring will be at the first

time of resolved influenza symptoms, if and only if after this observation there is no recording of non-resolved influenza symptoms (ignoring missing recordings). If there are no recordings of resolved symptoms satisfying this criterion, the time of censoring is the first possible time point a diary entry could have been made after the last observation of the presence of influenza, which is 20:00 on the same day if the last observation was a morning diary entry (from 3:01 until 15:00), 8:00 the next day if the last entry was an evening diary (from 15:01 until 03:00) (Day 1 until Day 14, morning). If the last observation of the presence of influenza is on Day 14 in the evening or after day 14 then the time of censoring is the time of the last diary entry + 24 hours. One exception is censoring at the Day 28 Visit (last study day for the subject). If the subject is not recovered on this day, the time of the last diary entry will be taken as the time of censoring.

Subjects who discontinue the study before resolving influenza symptoms and have an adverse events being reported as influenza complication ongoing on the day of discontinuation of the study will be censored at day 28, 20:00.

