The time to influenza A viral negativity (see definition in section 4.2.2) measured by viral load and viral titer will be correlated with the following clinical measures (see definitions in sections 4.2.3 and 4.2.6):

1. Time to resolution of symptoms (7 primary symptoms)
2. Time to resolution of symptoms (All symptoms)
3. Time to return to usual activity,
4. Time to return to usual health and
5. Time to significant reduction in influenza symptom severity

Scatter plots with smoother curve will be shown per treatment group for the above mentioned correlations. An additional table will be provided showing the spearman correlation coefficients.

- **Correlation between the viral load, viral titer and severity of clinical symptoms**

The post-baseline log₁₀ values of viral load and post-baseline log₁₀ values of viral titer from day 2 to day 7 will be correlated with the following severity of clinical symptoms (see definitions in sections 4.2.3 and 4.2.6):

1. Flu-iiQTM daily average symptom score post-baseline from day 2 to day 7
2. FLU-PRO total score post-baseline from day 2 to day 7

Scatter plots with smoother curve will be shown per treatment group for the above mentioned correlations. An additional table will be provided showing the spearman correlation coefficients.

- **Correlation between baseline viral load, baseline viral titer and clinical symptoms**

The baseline viral load and baseline viral titer will be correlated with the following clinical measures (see definitions in sections 4.2.3 and 4.2.6):

1. Time to resolution of symptoms (7 primary symptoms)
2. Time to resolution of symptoms (All symptoms)
3. Time to return to usual activity,
4. Time to return to usual health and
5. Time to significant reduction in influenza symptom severity

Scatter plots with smoother curve will be shown per treatment group for the above mentioned correlations. An additional table will be provided showing the spearman correlation coefficients.

4.2.9. *Other Outcomes*

▪ **Time to hospital discharge**

The time to hospital discharge will be calculated from the date of first study drug intake during hospitalization up to the date of discharge. Subjects still hospitalized at the end of the study (end date of hospitalization missing or after trial termination) will be censored at the trial termination date.

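### SAP 4.2.8 plans plain Spearman coefficients with no handling of repeated days or of censored times; if days are pooled, shared recovery alone gives a positive coefficient

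*SAP*

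**What the plan says.** SAP 4.2.8 has three blocks.

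- **First block.** Time to viral negativity, "measured by viral load and viral titer will be correlated with the following clinical measures": two times to symptom resolution, time to usual activity, time to usual health, and time to significant symptom reduction.
- **Second block.** Post-baseline log10 viral load and "values of viral titer from day 2 to day 7 will be correlated with the following severity of clinical symptoms". The scores are the Flu-iiQ daily average and the "FLU-PRO total score post-baseline from day 2 to day 7".
- **Third block.** Baseline viral load and titer against the same five times.

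The output is the same for each block: "Scatter plots with smoother curve will be shown per treatment group for the above mentioned correlations", and "An additional table will be provided showing the spearman correlation coefficients". Neither a study-day breakdown nor a within-subject step is mentioned.

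The times carry censoring rules elsewhere. For viral negativity (SAP 4.2.2), where no confirmed negative occurs, "a subject will be censored at the time of the last observed nonnegative swab + 1 day". For symptom resolution (SAP 4.2.3), "In cases where there are no sufficient recordings of resolved influenza as defined above, the endpoint will be censored". SAP 4.2.6 has similar rules for the FLU-PRO times. Section 4.2.8 refers back to these definitions but does not say what becomes of a censored subject.

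**The concern.** Two separate problems arise, in different blocks.

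**Repeated days (second block only).** Viral load and symptom scores both fall as patients recover. If all Day 2-7 pairs go into one coefficient, early pairs are high on both and late pairs low on both. The coefficient is then positive even if, on any given day, patients with more virus are no sicker than the others.

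**Censoring (first and third blocks only).** Spearman has no censoring indicator. A censored time is either ranked as if it were the event time or dropped. Both distort the coefficient.

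The correlation of viral decline with symptom change is a listed exploratory objective (Protocol 2.1, SAP 1.1). At stake is whether a coefficient produced by ordinary recovery, or by patients leaving observation early, is read as a link between antiviral and clinical effect.

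**Working it through.** The documents state no coefficient, precision or sample size for these correlations, so there is no figure to reproduce.

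**Is pooling the natural reading?** Where the SAP wants an analysis by time point it says so: in 4.2.2 the logistic model for viral negativity is fitted per time point. Where it wants within-subject structure it says that too: the rate-of-decline model has a random intercept and slope. Section 4.2.8 has neither, and correlates one Day 2-7 range with another. Pooling is thus the natural reading, though it is not written.

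**Second block: size under no association.** Assumed, not from the documents: viral load starts at 6 log10, SD 1.0 between and 0.7 within subjects; symptom score starts at 1.8, SD 0.5 and 0.3; both decline linearly; the two are independent between and within subjects. Days 2-7 have variance (6² − 1)/12 = 2.917. Ignoring the detection limit, the pooled (Pearson) correlation for slopes *a* and *b* per day is

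r = 2.917·a·b / √[(1.0² + 0.7² + 2.917·a²)(0.5² + 0.3² + 2.917·b²)]

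For a = 0.5 and b = 0.15: 0.2187 / √(2.219 × 0.4056) = 0.23. The simulation used Spearman, the SAP's imputations of 0 and 2.12, 20 to 60 subjects per arm and 400 data sets per setting:

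| Slopes per day (virus, symptoms) | Formula | Simulated, pooled | Simulated, by day (mean) |
|---|---|---|---|
| 0, 0 | 0 | about 0.00 | about 0.00 |
| 0.3, 0.1 | 0.11 | 0.10-0.13 | −0.01 to 0.01 |
| 0.5, 0.15 | 0.23 | 0.23-0.24 | about 0.00 |
| 0.7, 0.2 | 0.35 | 0.36-0.37 | −0.02 to 0.01 |

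The formula contains no *n*, so more subjects do not remove the bias.

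**Second block: masking.** With a true between-subject correlation of −0.5 and slopes 0.5 and 0.15, the covariance between subjects is −0.5 × 1.0 × 0.5 = −0.25 and the trend adds +0.2187, so they nearly cancel. Simulated: −0.02 pooled against −0.34 by day.

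**Does a within-subject correlation cure this?** Not by itself: it removes the between-subject variance and keeps the trend. The sum of squared day deviations is 17.5, with 5 degrees of freedom per subject, so

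r = 17.5·a·b / √[(5·0.7² + 17.5·a²)(5·0.3² + 17.5·b²)]

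For a = 0.5 and b = 0.15: 1.3125 / √(6.825 × 0.8438) = 0.55. Across the three declining settings this gives 0.33, 0.55 and 0.69; simulation gave 0.33, 0.54 and 0.67. These are larger than the pooled values. Adjusted for study day, the simulated value was about 0.00.

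**First block: censoring.** Two lognormal event times, n = 40, 2,000 data sets, censored times ranked as if observed. Early censoring was assigned to 10% to 40% of subjects (assumed).

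| Censoring pattern | Uncensored Spearman 0.47 becomes | Uncensored Spearman 0 becomes |
|---|---|---|
| Day 14 (swabs) and Day 28 (diary) limits only | 0.47 | 0.00 |
| Independent for the two times | 0.43 to 0.31 | about 0.00 |
| Early end of swabbing only | 0.43 to 0.32 | about 0.00 |
| Shared early withdrawal | 0.55 to 0.71 | 0.14 to 0.48 |

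The third block was not simulated. Only one of its variables is censored, so one-sided censoring is the nearest analogue and shared withdrawal does not arise in the same form. Dropping censored subjects was not simulated either; it keeps the subjects with shorter times, and so selects on the outcome.

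**Features of the design that bear on this.** Central swabs are daily in hospital, but after discharge the only scheduled one within Days 2-7 is the Day 5 visit (Protocol Time and Events Schedules), so pooled pairs over-represent patients who stay in hospital. A subject who discontinues unresolved with an ongoing influenza complication is censored at Day 28, 20:00 for symptoms, but one day after the last non-negative swab for virus. Ranked as observed, that makes an artificial pair.

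**The case against.** The strongest reply is that the SAP does not say what is being criticised. It never states that days are pooled or that censored times enter as observed. Its wording also fits one coefficient per day, and censored subjects could be dropped. SAP 3.4 leaves details of individual displays to the Data Presentation Specifications, which are not available here. This stands to the extent that pooling and naive censoring are inferences and must be described as such. It does not dispose of the point: which association is estimated is an analysis choice rather than a layout choice, and the SAP states such choices elsewhere.

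Second, the block whose heading matches the exploratory objective is the first, with one value per subject. The pooling bias does not touch it. That is correct, and the second-block figures should not be quoted for it.

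Third, the consequence is limited. SAP 4.2 plans no formal hypothesis testing, 4.2.8 mentions no p-value or confidence interval, and treatment effects on virology and symptoms have their own survival and mixed-model analyses. This also stands.

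Three stronger conclusions are tempting and are not supported:

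- **That the analysis is bound to report an association.** There is no decision rule, and the size depends on declines that the documents do not give; with no trend it is about zero.
- **That censoring always understates the association.** The direction depends on the censoring pattern.
- **That an error rate is inflated.** None is claimed. A p-value attached later to the pooled coefficient would be unreliable: in simulation, nominal p < 0.05 occurred in 27-32% of data sets from clustering alone and in 36-100% with trends.

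**Conclusion.** The concern holds in limited form. SAP 4.2.8 specifies plain Spearman coefficients with no handling of repeated days in the second block and none of censoring in the first and third. If days are pooled, as the text most naturally reads, a shared recovery trend alone yields about 0.1 to 0.37 under the assumed declines, and a real negative association can disappear. If censored times are ranked as observed, the first-block coefficient can be biased either way; in the third block, attenuation is the expected result when censoring does not depend on baseline virus. All slopes, SDs and censoring fractions are assumptions. The harm is a potentially misleading descriptive coefficient for an exploratory objective. It is a minor point, worth making because a better method is nearly free.

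**What to change.** - **Second block.** Report Spearman coefficients by study day, Days 2 to 7, with the number of pairs on each day. If a within-subject correlation is added, adjust it for study day; unadjusted, it is more biased than pooling.
- **First block.** Replace plain Spearman with a rank correlation that allows for censoring in both times, or fit a Cox model for symptom resolution with viral negativity as a time-dependent covariate. The Cox model asks a slightly different question: whether resolution becomes more likely once virus is gone.
- **Third block.** Use a censoring-aware rank correlation, or a Cox model with baseline viral load or titer as covariate.
- **Reporting.** State the number of censored subjects beside each time-based result.

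The cost is SAP wording and a little programming; no new data are needed. The statistical price is precision. Under no association the standard error of a Spearman coefficient is about 1/√(n − 1): 1/√39 = 0.16 with 40 subjects and 1/√19 = 0.23 with 20, and larger on days when few patients remain in hospital. By-day coefficients on those days describe mainly the patients still hospitalised, which the table should say.
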